7.6 Repeat Questionnaires & Attention Bias Tasks

After the tDCS session participants will repeat two of the questionnaires (PANAS and AMS) and both attention bias tasks.

8 Study Questionnaires

Participants will be asked to complete the following self-report questionnaires:

- **Beck Depression Inventory (BDI-II)**: a brief, criteria-referenced assessment for measuring depression severity. The BDI-II consists of 21 items to assess the intensity of depression. Each item is a list of four statements arranged in increasing severity about a particular symptom of depression.
- **Beck Anxiety Inventory (BAI)**: a brief, criteria-referenced assessment for measuring anxiety severity and level. Participants respond to 21 items rated on a scale from 0 to 3. Each item is descriptive of subjective, somatic, or panic-related symptoms of anxiety. BAI has been found to discriminate well between anxious and non-anxious diagnostic groups in a variety of clinical populations.
- **Hamilton Depression Rating Scale (HAM-D)**: 17-item measure that was designed to assess frequency and intensity of depressive symptoms in patients with MDD. This measure contains somatic and suicidal ideation items and has demonstrated reliability, validity, and efficiency in adult populations
- **Symptoms of Major Depressive Disorder Scale (SMDDS)**: a brief measure for adults with MDD and measures specific symptom dimensions. The measure has good psychometric properties including high reliability and validity.
- **Analog Mood Scale (AMS)**: is a brief measure of positive and negative mood consisting of three questions (i.e., “How anxious are you?”, “How sad are you?”, and “How happy are you?”). Participants were told to indicate their present mood by identifying a location on a horizontal line divided into 30 equally distanced segments labeled 1 (not at all) to 30 (very much).
- **Positive and Negative Affect Schedule (PANAS-SF)**: a self-report questionnaire that consists of two 10-item scales (20 items total) to measure both positive and negative affect.

9 Safety and Adverse Events

9.1 Definitions

Unanticipated Problems Involving Risk to Subjects or Others

Any incident, experience, or outcome that meets all of the following criteria:

- Unexpected in nature, severity, or frequency (i.e. not described in study-related documents such as the IRB-approved protocol or consent form, the investigators brochure, etc)
- Related or possibly related to participation in the research (i.e. possibly related means there is a reasonable possibility that the incident experience, or outcome may have been caused by the procedures involved in the research)

CONFIDENTIAL

- Suggests that the research places subjects or others at greater risk of harm (including physical, psychological, economic, or social harm).

Adverse Event

An **adverse event** (AE) is any symptom, sign, illness or experience that develops or worsens in severity during the course of the study. Intercurrent illnesses or injuries should be regarded as adverse events. Abnormal results of diagnostic procedures are considered to be adverse events if the abnormality:

- results in study withdrawal
- is associated with a serious adverse event
- is associated with clinical signs or symptoms
- leads to additional treatment or to further diagnostic tests
- is considered by the investigator to be of clinical significance

Serious Adverse Event

Adverse events are classified as serious or non-serious. A **serious adverse event** is any AE that is:

- fatal
- life-threatening
- requires or prolongs hospital stay
- results in persistent or significant disability or incapacity
- a congenital anomaly or birth defect
- an important medical event

Important medical events are those that may not be immediately life threatening, but are clearly of major clinical significance. They may jeopardize the subject, and may require intervention to prevent one of the other serious outcomes noted above. For example, drug overdose or abuse, a seizure that did not result in in-patient hospitalization, or intensive treatment of bronchospasm in an emergency department would typically be considered serious.

All adverse events that do not meet any of the criteria for serious should be regarded as **non-serious adverse events**.

Preexisting Condition

A preexisting condition is one that is present at the start of the study. A preexisting condition should be recorded as an adverse event if the frequency, intensity, or the character of the condition worsens during the study period.

General Physical Examination Findings

At screening, any clinically significant abnormality should be recorded as a preexisting condition. At the end of the study, any new clinically significant findings/abnormalities that meet the definition of an adverse event must also be recorded and documented as an adverse event.

Post-study Adverse Event

All unresolved adverse events should be followed by the investigator until the events are resolved, the subject is lost to follow-up, or the adverse event is otherwise explained. At the last scheduled visit, the investigator should instruct each subject to report any subsequent event(s) that the subject, or the subject's personal physician, believes might reasonably be related to participation in this study. The investigator should notify the study sponsor of any death or adverse event occurring at any time after a subject has discontinued or terminated study participation that may reasonably be related to this study. The sponsor should also be notified if the investigator should become aware of the development of cancer or of a congenital anomaly in a subsequently conceived offspring of a subject that has participated in this study.

9.2 Recording of Adverse Events

At each contact with the subject, the investigator must seek information on adverse events by specific questioning and, as appropriate, by examination. Information on all adverse events should be recorded immediately in the source document, and also in the appropriate adverse event module of the case report form (CRF). All clearly related signs, symptoms, and abnormal diagnostic procedures results should be recorded in the source document, though should be grouped under one diagnosis.

CONFIDENTIAL

All adverse events occurring during the study period must be recorded. The clinical course of each event should be followed until resolution, stabilization, or until it has been determined that the study treatment or participation is not the cause. Serious adverse events that are still ongoing at the end of the study period must be followed up to determine the final outcome. Any serious adverse event that occurs after the study period and is considered to be possibly related to study participation should be recorded and reported immediately.

9.3 Reporting of Serious Adverse Events and Unanticipated Problems

For Narrative Reports of Safety Events

If the report is supplied as a narrative, the minimum necessary information to be provided at the time of the initial report includes:

- Study identifier
- Study Center
- Subject number
- A description of the event
- Date of onset
- Current status
- Whether study treatment was discontinued
- The reason why the event is classified as serious
- Investigator assessment of the association between the event and study treatment

9.3.1 Investigator reporting: notifying the IRB

Federal regulations require timely reporting by investigators to their local IRB of unanticipated problems posing risks to subjects or others. The following describes the NYULMC IRB reporting requirements, though Investigators at participating sites are responsible for meeting the specific requirements of their IRB of record.

Report Promptly, but no later than 5 working days:

Researchers are required to submit reports of the following problems promptly but no later than 5 working days from the time the investigator becomes aware of the event:

- **Unanticipated problems including adverse events that are unexpected and related**
 - *Unexpected: An event is “unexpected” when its specificity and severity are not accurately reflected in the protocol-related documents, such as the IRB-approved research protocol, any applicable investigator brochure, and the current IRB-approved informed consent document and other relevant sources of information, such as product labeling and package inserts.*
 - *Related to the research procedures: An event is related to the research procedures if in the opinion of the principal investigator or sponsor, the event was more likely than not to be caused by the research procedures.*
 - *Harmful: either caused harm to subjects or others, or placed them at increased risk*

Other Reportable events:

The following events also require prompt reporting to the IRB, though **no later than 5 working days**:

- **Complaint of a research subject** when the complaint indicates unexpected risks or the complaint cannot be resolved by the research team.
- **Protocol deviations or violations** (includes intentional and accidental/unintentional deviations from the IRB approved protocol) for any of the following situations:
 - *one or more participants were placed at increased risk of harm*
 - *the event has the potential to occur again*
 - *the deviation was necessary to protect a subject from immediate harm*
- **Breach of confidentiality**
- **Incarceration of a participant** when the research was not previously approved under Subpart C and the investigator believes it is in the best interest of the subject to remain on the study.

CONFIDENTIAL

- ***New Information indicating a change to the risks or potential benefits*** of the research, in terms of severity or frequency. (e.g. analysis indicates lower-than-expected response rate or a more severe or frequent side effect; Other research finds arm of study has no therapeutic value; FDA labeling change or withdrawal from market)

Reporting Process

The reportable events noted above will be reported to the IRB using a Reportable New Information submission and will include a description of the event with information regarding its fulfillment of the above criteria, follow-up/resolution, and need for revision to consent form and/or other study documentation. Copies of each report and documentation of IRB notification and receipt will be kept in the Clinical Investigator's study file.

10 Study Oversight

10.1 Data Safety Monitoring

It is the responsibility of the Principal Investigator to oversee the safety of the study. This safety monitoring will include careful assessment and appropriate reporting of adverse events as noted above. Data safety monitoring will occur at least every 4 months and will include PI review of reports of tDCS side effects including skin irritation, itching, warming, and discomfort, emotional distress, protocol adherence, regulatory documentation, enrollment (e.g. rate of enrollment, screen fails, withdrawals, etc.), unanticipated problems, and any issues that may arise during the course of research.

10.2 Medical Monitoring

[name], MD, Director of the NYU MSCCC, will serve as medical monitor for this study. [name] will be responsible for determining SAE severity and relatedness.

10.3 Clinical Monitoring

N/A

10.4 Study Halting Rules

There are no predefined stopping rules for this study.

10.5 Participant Withdrawal or Termination

10.5.1 Reasons for Withdrawal or Termination

Participants are free to withdraw from participation in the study at any time upon request. An investigator may terminate participation in the study if:

- Any clinical adverse event (AE), laboratory abnormality, or other medical condition or situation occurs such that continued participation in the study would not be in the best interest of the participant
- The participant meets an exclusion criterion (either newly developed or not previously recognized) that precludes further study participation
- The participant is non-compliant with study procedures

10.5.2 Handling of Participant Withdrawals or Termination

Data of participants who withdraw or are terminated from the study may be kept for analysis if the data is usable (as determined PI).

10.5.3 Premature Termination or Suspension of Study

This study may be temporarily suspended or prematurely terminated if there is sufficient reasonable cause. If the study is prematurely terminated or suspended, the PI will promptly inform the IRB and will provide the reason(s) for the termination or suspension.

Circumstances that may warrant termination or suspension include, but are not limited to:

CONFIDENTIAL

- Determination of unexpected, significant, or unacceptable risk to participants
- Demonstration of efficacy that would warrant stopping
- Insufficient compliance to protocol requirements
- Data that are not sufficiently complete and/or evaluable
- Determination of futility

Study may resume once concerns about safety, protocol compliance, data quality are addressed and satisfy the IRB.

11 Statistical Considerations

11.1 Study Hypotheses

A single-session tDCS to the left DLPFC will reduce negative attention bias in people with mild to moderate depression. There will be cohort differences across mildly depressed vs. healthy controls with easy anagram vs. healthy controls with difficult anagram (situational stressor) where the reduction of negative attention bias would be greatest in the depressed group compared to the healthy controls.

The primary objective of this study is exploratory data collection. These pilot study findings will be the necessary first step to inform future study design and hypotheses. We are collecting the healthy control pilot data to better interpret the pilot findings in patients with depression, and to provide us with expected ranges of change in our task measures. This inclusion of the anagram task is exploratory to inform future study designs. The use of the challenging anagram task is based from literature where the same paradigm has been used in healthy controls to study temporary states of negative affect (e.g., frustration, anxiety; Myruski et al., 2021).

11.2 Sample Size Determination

The primary objective of this study is to test change in negative attention bias in people with mild to moderate depression following a single session of DLPFC tDCS, and see if their outcomes differ from that of healthy controls.

This is a pilot study to assess the feasibility of a single-session tDCS in a small sample, and the findings will provide preliminary evaluation of effect and inform power analyses for use in a clinical trial design.

A total of $N = 75$ ($n=25$ participants for each group) will be enrolled to obtain evaluable target of $N=60$ ($n = 20$ for each group) based on the estimated number of eligible participant for each group contacts across the study period.

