Statistical Analysis	Pre-post tDCS comparison analyses using t-tests and correlations

CONFIDENTIAL

Schematic of Study Design

Pre-Screen	
• Eligibility pre-screen to determine general eligibility including BDI-II screen
Study Visit	
• Obtain Informed Consent• Mini International Neuropsychiatric Interview (MINI) (Screening)• Beck Depression Inventory (BDI-II) (Screening)• Beck Anxiety Inventory (BAI)• Hamilton Depression Rating Scale (HAM-D)• Symptoms of Major Depressive Disorder Scale (SMDDDS)• Healthy controls will complete a brief computer-based word puzzle task before the tDCS session, assigned to one of two conditions: difficult/unsolvable or easier
Pre-tDCS Administration	
• Positive and Negative Affect Schedule-SF (PANAS);• Analog Mood Scale (AMS)• Dot Probe Task (DP) and Visual Search (VS) Task
tDCS Administration	
• tDCS tolerability test• 30 minutes of tDCS (up to 2.0mA)
Post-tDCS Administration	
• PANAS• AMS• DP and VS Tasks

CONFIDENTIAL

Key Roles

Principal Investigator:

[name]
NYU Langone Health
Department of Neurology
[name]
[contact]
[contact]

Sub-Investigators:

[name]
NYU Langone Health
Department of Neurology
[name]
[contact]
[contact]

[name]
Department of Neurology, NYU Langone Health
[name]
[name]
[contact]
[contact]

1 Introduction, Background Information and Scientific Rationale

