on the scalp to the target regions of interest. tDCS has been extensively demonstrated to be a safe and tolerable treatment, with no serious adverse events reported across clinical trials to date (Bikson et al., 2016).

In treatment of MDD, the use of tDCS is based on evidence of an interhemispheric functional asymmetry in depressive states that leads to a hypoactivation of the left dorsolateral prefrontal cortex (DLPFC) and hyperactivation of the right DLPFC (Grimm et al., 2008). The DLPFC is connected to the frontoparietal network (FPN), which has been found to be underactivated in depression (Korgaonkar et al., 2013). Most importantly, past studies suggest that the use of tDCS over the DLPFC may increase cognitive performance of people with depression, mainly due to the fact that DLPFC is involved in complex cognitive processes and attentional network (Brunoni & Vanderhasselt, 2014; Dedoncker et al., 2016). This further implies that application of tDCS in the DLPFC may also modulate attention associated with negative attention bias associated with depression, as well as potentially reducing depressive symptoms.

Recent studies have noted that a single session of DLPFC tDCS administration can reduce AB in patients with anxiety disorders (Heeren et al., 2017), but more research is needed to support the impact of short-term (i.e., single-session) tDCS in modifying or reducing AB, more specifically in depression.

In summary, tDCS has an extensive record of safety and tolerability. A large body of research has demonstrated its efficacy in reducing depressive symptoms following cumulative daily treatment sessions (e.g., 20 or more). While there is no clinical treatment benefit expected from a single session of tDCS, no study to date has yet to evaluate the immediate effect of single-session DLPFC tDCS in depression-related AB. This study will be one of the first studies to evaluate the efficacy of the single-session tDCS on depression-related attention bias and depressive mood and symptoms.

Rationale

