Risks Associated with Mood Questionnaires: Completing questionnaires may produce some emotional distress in some participants. While we do not anticipate this to be a significant issue, participants will be allowed to take breaks as needed and may stop answering questions at any time without affecting their enrollment.

Risks Associated with Computer-Based Word Puzzle Task: If participants are assigned to the difficult/unsolvable condition, they may experience situational frustration or emotional discomfort. While we expect any discomfort to be brief and transitory, participants will be able to stop if the task at any point.

Risks Associated with Attention Bias Task: There are no anticipated risks from completing a computerized attention bias tasks.

Other risks:

There is minimal risk of breach of confidentiality. All data will be kept strictly confidential and stored in locked cabinets located at NYU Ambulatory Care Center (ACC), [name]. Electronic data will be stored on secure, password-protected, NYU Langone computers. Participants will be assigned a unique ID that will be used on all data collection instruments.

Unforeseeable risks: There may be risks associated with tDCS that are currently not known.

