4.1 Description of Study Design

In this prospective pilot study we will recruit 25 female participants, ages 18-45 (inclusive), with mild to moderate depression (based on BDI-II score range 14-19 for mild and 20-28 for moderate) as well as 50 healthy control (defined by a BDI > 14) females of the same age range (18-45) to determine if a single-session of tDCS can alter negative attention bias. With the healthy control group, the recruited participants will be assigned to either

CONFIDENTIAL

the easy (n = 25) or difficult/unsolvable (n = 25) pre-tDCS word puzzle task condition. The group assignment will be pseudo-randomized (counterbalanced; e.g., alternating easy and difficult anagram conditions). The primary objective is to study if single-session tDCS will affect attention bias in depression and is not meant to treat depression. Subjects may or may not be receiving treatment for mild-moderate depression. If potential participant is severely depressed during the screening, standard clinical procedures will be used such as advising them to contact their treating physician and/or providing them a crisis hotline number (SAMHSA's National Helpline: [name], or to NYU Langone Psychiatry Associates at [contact].

For this initial pilot study, we are measuring subtle changes in response time latency at the millisecond level for attention bias. Because demographic factors of both age and sex are known to influence response times on attention tasks (Dykiert, Der, & Deary, 2012; Joormann & Gotlieb, 2007), we will limit the contribution of these factors in this initial pilot study.

The study will consist of a single 2.5 hour research visit that will take place at the NYU Ambulatory Care Center ([name]). After written informed consent is obtained (outlined in section 13.1), participants will have an eligibility screening which will include a semi structured interview (MINI). Eligible participants will complete depression and mood self-report questionnaires, two attention bias tasks (dot-probe and visual), and a single 30-minute tDCS session. Total study duration (including analysis, etc.) will be 1 year.

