Participant preparation for tDCS session: The trained study technician will prepare the stimulation electrodes as detailed below:

- Two single-use sponge patches will be (1) inserted in the patch supporters and (2) soaked with saline solution.
- The patches will be then attached to the headband in the positions corresponding to the frontal region. The red patch (anode) will be located on the left frontal region while the blue patch (cathode) on the right region frontal region.
- The headband will be then positioned on the participant's head.
- The stimulation module will be then attached to the electrode cables.

CONFIDENTIAL

- The study technician will connect the stimulation module via Bluetooth to the management station and then will be ready to initiate the stimulation session.

tDCS session: Participants will complete a single 30 minutes tDCS session targeting the left DLPFC while sitting in a comfortable position. At the end of the tDCS session possible side effects experienced during the tDCS session will be recorded along with their intensity (rated using the visual analogue scale, 0-10) and duration. The session can be aborted at any time for any reason if the participant wishes.

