11.3 Statistical Methods

For the study hypothesis to examine the preliminary effect of a single-session tDCS on depression on negative attention bias, we will use the calculated latency response times pre-tDCS and post-tDCS using the DP and VS tasks and compare change using a paired sample's t-test for each measure. Further, to compare across the groups, we will use ANOVA for before and after effect of tDCS on negative attention bias across the three groups.

As secondary and exploratory, we will also test change in pre- to post- ratings of depressive symptoms and affect. These findings will be collected to inform the power analyses for a larger controlled trial.

12 Source Documents and Access to Source Data/Documents

Source data is all information, original records of clinical findings, observations, or other activities in a study necessary for the reconstruction and evaluation of the study. Source data are contained in source documents. Examples of these original documents, and data records include: hospital records, clinical and office charts, laboratory notes, memoranda, evaluation checklists, pharmacy dispensing records, recorded data from

CONFIDENTIAL

automated instruments, copies or transcriptions certified after verification as being accurate and complete, subject files.

The study case report form (CRF) is the primary data collection instrument for the study. All data requested on the CRF must be recorded. All missing data must be explained. If a space on the CRF is left blank because the procedure was not done or the question was not asked, write "N/D". If the item is not applicable to the individual case, write "N/A". All entries should be printed legibly in blue or black ink. If any entry error has been made, to correct such an error, draw a single straight line through the incorrect entry and enter the correct data above it. All such changes must be initialed and dated. DO NOT ERASE OR WHITE OUT ERRORS. For clarification of illegible or uncertain entries, print the clarification above the item, then initial and date it.

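### Every group is stimulated between two runs of the same tasks, so the pre-post change mixes tDCS with retest change and should neither be reported as the tDCS effect nor set the target difference of the later controlled trial

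*Combined protocol and SAP*

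**What the plan says.** Section 7.5 gives one active session and no alternative to it: "Participants will complete a single 30 minutes tDCS session targeting the left DLPFC while sitting in a comfortable position". The Schematic of Study Design shows that the controls are stimulated too: "Healthy controls will complete a brief computer-based word puzzle task before the tDCS session, assigned to one of two conditions". Only the easy or difficult anagram is allocated, by alternation within the controls (section 4.1). Stimulation is not allocated. Both attention tasks are run before the session and repeated after it (sections 6.2 and 7.6).

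Section 11.3 compares pre and post by a paired t-test for each measure, to examine the preliminary effect of tDCS. It then uses an ANOVA across the three groups, described as the before-and-after effect of tDCS. Section 11.1 hypothesises that tDCS reduces negative bias in the depressed group, with the largest reduction there. Section 1.1 says that the study will be among the first to "evaluate the efficacy of the single-session tDCS on depression-related attention bias".

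On use of the results, section 11.2 says "the findings will provide preliminary evaluation of effect and inform power analyses for use in a clinical trial design", and section 11.3 adds "These findings will be collected to inform the power analyses for a larger controlled trial". Section 11.1 says that the control data are collected partly "to provide us with expected ranges of change in our task measures". None of these sections says how retest change will be separated from tDCS, or which quantities go into the later power analysis.

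**The concern.** A participant who repeats a reaction-time task about half an hour later may change through practice, habituation to the faces or fatigue, with or without stimulation. Nobody in this study repeats the tasks unstimulated, so the paired test estimates tDCS plus retest change and cannot separate them. A controlled trial estimates active minus control. If the uncontrolled change is carried over as its expected difference, the later trial is sized on a different quantity.

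The exposure depends on the measure. Section 4.2 names attention bias scores as the endpoint. In a difference between latencies to two target types, a uniform speeding cancels. Section 7.4.2, however, makes mean response time the visual-search outcome, and section 11.3 speaks of latency response times. Raw latencies take the whole of any speeding or slowing.

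There is a separate issue in one control group. If the difficult anagram comes before the baseline tasks, that group's baseline is taken under a stressor, and its later change also includes recovery from it.

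**Working it through.** **The plan's own figure.** 25 enrolled and 20 evaluable per group imply a loss of 5/25 = 20%. Then 20/(1 − 0.20) = 25, and 3 × 25 = 75, as stated. The plan gives no alpha, power, SD or effect size, so there is no power figure to reproduce.

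**Assumptions for what follows.** Two-sided alpha 0.05; shifts in units of the SD of change; n = 20 evaluable per group (sections 5.5 and 11.2). The size of the retest shift is assumed, because the documents do not give one.

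**Step 1: paired test with no tDCS effect.** The statistic follows a noncentral t with 19 degrees of freedom and noncentrality d√n, where √20 = 4.472. The critical value is 2.093.

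| Retest shift d | Noncentrality | Rejection rate |
|---|---|---|
| 0.1 | 0.447 | 7% |
| 0.2 | 0.894 | 14% |
| 0.3 | 1.342 | 25% |
| 0.5 | 2.236 | 56% |

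The nominal rate is 5%.

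**Step 2: does the three-group ANOVA help?** One-way ANOVA on change scores, 3 × 20, 20,000 simulated studies. If tDCS works equally in all groups (0.5 SD each), it rejects in about 5%: an effect common to all groups is invisible to it. If tDCS does nothing and only the difficult-anagram group changes, by 0.3, 0.5 or 0.8 SD, it rejects in about 15%, 34% or 73%. A main effect of time from the same model would show a common shift, but with retest change inside it, as in Step 1.

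**Step 3: consequence for a later 1:1 controlled trial.** Assume it analyses change scores with the same SD and is sized on 0.5 SD. Noncentrality is d√(n/2) with 2n − 2 degrees of freedom. For 80% power, n = 64 per arm: 0.5 × √32 = 2.828, power 80%.
- If 0.1 SD of the 0.5 is retest, the true difference is 0.4: 0.4 × 5.657 = 2.263, power 61%.
- If half is retest, the true difference is 0.25: 0.25 × 5.657 = 1.414, power 29%; 253 per arm would be needed for 80%.

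**Step 4: precision, apart from bias.** An observed standardised change of 0.5 at n = 20 has a 95% interval of 0.03 to 0.96 (noncentral t). This is sampling error and is no evidence of retest bias, but it is a second reason not to size a trial on the point estimate.

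**Step 5: order of the anagram.** The schematic puts the puzzle in the block before the pre-tDCS measures, and section 7.3 (anagram) comes before section 7.4 (tasks). The visit list in section 6.2 leaves the anagram out. The order is therefore implied, not stated.

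**The case against.** This is openly an exploratory, uncontrolled pilot. Section 11.2 gives feasibility as an aim, the effect is called preliminary, and a controlled trial is foreseen. That lowers the seriousness. It does not answer the point, because the effect wording and the power use stand in the same sections.

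The power use could be read more narrowly. The SD and the evaluable rate also inform power, nothing says that the point estimate becomes the target difference, and the sentence in section 11.3 follows directly on the secondary mood and affect analyses. That is fair. But section 11.2 joins evaluation of effect to the power analyses and sets no limit on what is carried forward.

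The group contrast also deserves credit: if retest change is equal in all groups, depressed versus easy-anagram removes it. What remains is a difference in response between groups, not tDCS against none.

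Three stronger readings are tempting, and the documents do not support them.
- A reader might infer that the bias runs upward. No direction is documented, practice and fatigue can oppose each other, and bias scores cancel uniform speeding.
- A reader might infer that stress recovery inflates the depressed group's result. Only the difficult-anagram controls receive the stressor, so it cannot enter that paired test. On the second hypothesis it works the other way: a reduction in a control group makes it harder for the depressed group to show the largest. The phrase "we expect any discomfort to be brief and transitory" in section 2.1 is also a statement about discomfort, not about attention bias.
- A reader might infer that the plan presents the controls as a no-treatment reference. Section 11.1 never says so. Ranges of change in stimulated healthy women are legitimate data; the sentence needs clarifying, not deleting.

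**Conclusion.** The concern stands as a matter of what may be claimed and carried forward. The design cannot identify an effect of tDCS, because neither the paired test nor the group comparison contrasts stimulation with its absence. False attribution at n = 20 ranges from 7% to 56% over assumed retest shifts of 0.1 to 0.5 SD, so it may be slight or serious. The later trial's power, nominally 80%, would be 61% or 29% if 0.1 or 0.25 of a 0.5 SD change is retest. These figures rest on assumed shifts and on equal SDs in the two trials; non-identifiability rests on neither. Raw latencies are more exposed than bias scores. Recovery from the stressor is a narrower issue, confined to the difficult-anagram controls and to contrasts with them, and conditional on the anagram preceding baseline. The plan should be changed, but a sham arm is not needed to make this pilot's statements supportable.

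**What to change.** In sections 11.1 to 11.3, with section 1.1 worded to match:

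1. Report the paired results as change after tDCS, not as an effect or efficacy of tDCS.
2. Take only the SD of change, the pre-post correlation and the evaluable rate into the later power analysis, and set its target difference on other grounds.
3. Say that the controls give ranges of change under active tDCS and are not a no-stimulation reference.
4. State when the anagram is given relative to the baseline tasks, and add it to the section 6.2 list. If it comes first, estimate the stressor effect as difficult versus easy at the pre-tDCS assessment, and do not read the difficult group's pre-post change as a response to tDCS.

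All of this uses data already planned. The cost is a weaker conclusion on the first hypothesis and one extra between-group comparison.
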